### **5.1.2 AE, concomitant medication, and other safety assessment date imputation**

Every effort will be made to get the missing information on partial dates. However, despite best efforts, some partial dates might still exist in the database. They will be listed as is. If needed in a calculation (e.g. duration), the standard Novartis Oncology imputation rules will be used.

**Table 5-1 Imputation of start dates (Adverse events, Concomitant Medications, etc.)**

Missing Element	Rule
day, month, and year	

• No imputation will be done for completely missing dates

day, month	

• If available year = year of study treatment start date then

◦ If stop date contains a full date and stop date is earlier than study treatment start date then set start date = 01JanYYYY

◦ Else set start date = study treatment start date.

• If available year > year of study treatment start date then 01JanYYYY

• If available year < year of study treatment start date then 01JulYYYY

day	

• If available month and year = month and year of study treatment start date then

◦ If stop date contains a full date and stop date is earlier than study treatment start date then set start date= 01MONYYYY.

◦ Else set start date = study treatment start date.

• If available month and year > month and year of study treatment start date then 01MONYYYY

• If available month and year < month year of study treatment start date then 15MONYYYY

**Table 5-2 Imputation of end dates (Concomitant Medications)**

Missing Element	Rule
day, month, and year	
*=last treatment date plus 30 days non > (death date, cut-off date)
 

• No imputation will be done for completely missing dates

Missing Element	Rule
	*=last treatment date plus 30 days non > (death date, cut-off date)
day, month	

• If partial end date contains year only, set end date = earliest of 31DecYYYY or end date of the on-treatment period*

day	

• If partial end date contains month and year, set end date = earliest of last day of the month or end date of the on-treatment period*

Any AEs and ConMeds with partial/missing dates will be displayed as such in the data listings.

Any AEs and ConMeds which are continuing as per data cut-off will be shown as 'continuing' rather than the end date provided.

## 5.2 Laboratory parameters

### 5.2.1 Derivations

The recalculated creatinine clearance will be calculated using the Schwartz formula (pediatric population at baseline). The MDRD derivation will be provided in the derived datasets only for possible future requests.

In the formulae below, CrCl denotes Creatinine Clearance, SCr denotes Serum Creatinine in  $\mu\text{mol/L}$ ; age in years is calculated from date of birth and date of the relevant blood sample. Weight and height are the last available measurements at the time of the relevant blood sample.

Schwartz formula (<18 years of age at beginning of the study),

$\text{CrCl} (\text{mL/min}) = (k \times \text{height}) / (\text{SCr} \times 0.01131)$  with

$k = 0.45$  for children <1 year based on current age

$k = 0.55$  for children from 1 to 12 years based on current age

$k = 0.55$  for girls  $\geq 13$  years based on current age

$k = 0.70$  for boys  $\geq 13$  years based on current age

The following rules will be applied for local lab data to derive the WBC differential counts when only percentages are available

Absolute value = (WBC count) \* (Value (%)) / 100

The unit of this absolute value will be the unit of WBC count.

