Population	
Up to 216 naïve and pre-treated (96 ICT naïve and up to 120 pre-treated ) male and female children and adolescents aged <math>\geq 2</math> and <math>< 18</math> years at enrollment with any transfusion-dependent anemia requiring chelation therapy due to iron overload, and a treatment goal to reduce iron burden will be included in this study. At least 96 (48 per treatment arm) patients should be iron chelation naïve.
 
The optional extension phase will give the patients who have participated and completed the 48 weeks core treatment phase as per protocol, the possibility to extend treatment with granules for a maximum of 5 years after completing the core treatment phase or until there is local access to new formulation (granules or FCT), whichever occurs first. All patients who choose to continue in the extension phase will receive granules during the optional extension phase.
 
There will be two study phases which include a 1 year core phase where patients will be randomized to a 48 week treatment period to either Deferasirox DT or granules, and an optional extension phase where all patients will receive the granules up to 5 years from entering extension phase. Patients who demonstrated benefit to granules or DT in the core phase, and/or express the wish to continue in the optional extension phase on granules, will be offered this possibility until there is local access to the new formulation (granules or FCT) or up to 5 years from entering extension phase, whichever occurs first.

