## 5.2 Inclusion criteria

Patients eligible for inclusion in this study have to meet **all** of the following criteria at screening Visit 1 and 2 unless otherwise specified:

1. Written informed consent/assent before any study-specific procedures. Consent will be obtained from parent(s) or legal guardians. Investigators will also obtain consent/assent of patients according to local guidelines.
2. Male and female children and adolescents aged  $\geq 2$  and  $< 18$  years. **[France: Male and female children and adolescent aged  $\geq 2$  and  $< 18$  years old, however children aged  $\geq 2$  and  $\leq 6$  years can be enrolled only when deferoxamine treatment is contraindicated or inadequate in these patients as per investigator decision.]** Applicable to core phase only. Once in the core phase patients can turn 18 years and still be considered eligible, also for participation in the optional extension phase.
3. Any transfusion-dependent anemia associated with iron overload requiring iron chelation therapy and with a history of transfusion of approximately 20 PRBC units and a treatment goal to reduce iron burden (300mL PRBC = 1 unit in adults whereas 4 ml/kg PRBC is considered 1 unit for children).
4. Serum ferritin  $> 1000$  ng/mL, measured at screening Visit 1 and screening Visit 2 (the mean will be used for eligibility criteria).
5. Patient has to have participated and completed the 48 weeks core phase treatment as per protocol (For optional extension phase eligibility only).

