**Table 6-2 Criteria for interruption and re-initiation of Deferasirox treatment**

Dose modifications for deferasirox	
Body weight	
Increase/decrease of weight by >10% compared to Visit 3 (baseline weight) or body weight at last dose adjustment due to change in patient's body weight	Dose of study medication needs to be adapted using Dosing Table (provided in Appendix 14.2 ). Only when weight changes with >10% compared to baseline weight or body weight at last dose adjustment due to change in patient's body weight, dose needs to be adapted. Smaller variations in body weight (<10%) during study, does not require adjustments in dose. In this case, baseline body weight can be used to calculate correct dose.
Investigations (Renal)	
Serum creatinine and/or creatinine clearance	
Single increase in serum creatinine $\geq 33\%$	Maintain dose level and repeat the assessment at next visit as clinically indicated
For pediatric patients: - Single increase $\geq 33\%$ above baseline value (visit 3/week1) and $> \text{ULN}$  For adult patients: - Increases by 33% or more above the baseline (visit 3/week1) measurement, repeat the serum creatinine within 1 week, and if still elevated by 33% or more	Deferasirox dose reduction by 10 mg/kg/day for the DT and by 7 mg/kg/day for the granules is necessary.
	If after a dose reduction, a progressive increase in serum creatinine beyond the ULN is observed, a treatment interruption is mandated. If after dose reduction/interruption, resolution of serum creatinine occurs ( $< 33\%$ ) at the next study visit and within normal limits, dose can be resumed again at 100%. If increase in serum creatinine reoccurs again within 2 months according to guidelines above, therapy needs to be reduced to 50% of the last dose. After 2 months, if the serum creatinine increase does not recur, study medication can be returned to 100% of the last dose.
Creatinine clearance between 40 and less 60 mL/min	Reduce dose with 50%. If after dose reduction, resolution of creatinine clearance occurs ( $> 60 \text{ ml/min}$ ), dose can be resumed again at 100%.
Creatinine clearance $< 40 \text{ mL/min}$ or serum creatinine increases $> 2$ times the age-appropriate ULN	Deferasirox therapy must be discontinued

Dose modifications for deferasirox	
Investigations (Hepatic)	
Isolated direct (conjugated) Bilirubin elevation	
> ULN – 2 x ULN	Maintain dose level

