#### 7.2.4.6.2 Clinical chemistry

Clinical chemistry samples will be collected during the core phase at Screening Visits 1 and 2, at Visit 3, 5-16, and 777 (EOT) and will be sent to the central laboratory, **[Egypt: Local laboratory]**. During the optional extension phase, monthly assessments will be done as per Exjade prescribing information as per [Table 7-2](#). Patients who were on the DT arm during core phase of study and decided to switch to granules as part of the optional extension phase will need to return weekly for the first month of the optional extension phase at Visits 18, 19 and 20 for serum creatinine and creatinine clearance monitoring. Thereafter they will follow the same schedule as patients who were on granules arm during the core phase. Clinical chemistry parameters to be measured are listed in [Table 7-4](#).

In accordance with the deferasirox label, serum creatinine, creatinine clearance, alkaline phosphatase, ALT/SGPT, AST/SGOT, direct (conjugated) bilirubin, indirect bilirubin, total bilirubin must be assessed in duplicate before the initiation of therapy to establish a reliable pre-treatment baseline.

In addition, serum creatinine will be measured weekly during the first three weeks (after the first study drug administration and at Visits 4, 5) and monthly thereafter (starting with Visit 6) till Visit 777 (EOT). During the optional extension phase, monthly assessments will be done as per Exjade prescribing information for patients previously on the granules arm of the core phase. Patients on the DT arm for the core phase of the study who have decided to switch to granules as part of the optional extension phase will need to return weekly for the first month at Visits

18, 19 and 20. Creatinine clearance will be calculated by the central lab **[Egypt: Local laboratory]** using the Schwartz formula for patients 17 years and younger and the Cockcroft-Gault formula for patients who turn 18 years old during the study, each time serum creatinine is collected.

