**Table 2-4      Definition of notable/extended ranges for key safety laboratory parameters**

Laboratory parameters	Criteria for notable/extended ranges
Platelet count	$< 100 \times 10^9/L$ (extended range $< 50 \times 10^9/L$ )
Absolute neutrophils	$< 1.5 \times 10^9/L$ (extended range $< 0.5 \times 10^9/L$ )
Serum creatinine	$> 33\%$ increase from baseline and $> ULN$ at two consecutive measurements at least 7 days apart

Laboratory parameters	Criteria for notable/extended ranges
Recalculated creatinine clearance	<60 mL/min at two consecutive measurements at least 7 days apart (extended range <40 mL/min at two consecutive measurements at least 7 days apart)
Urinary protein/urinary creatinine ratio	> 1.0 (mg/mg) at two consecutive measurements at least 7 days apart
ALT/AST	>5 x ULN and >2 x baseline (extended range >10×ULN and >2×baseline value)

Recalculated creatinine clearance will be calculated using the Schwartz formula (for pediatric population at baseline) described in [Section 5.2.1](#). The Modification of Diet in Renal Disease (MDRD) derivation will be provided in the derived datasets only for possible future requests.

A listing of all laboratory values with values flagged to show the corresponding range classifications relative to the laboratory reference ranges will be provided by laboratory data and treatment arm based on Safety set 4. Assessment day relative to first dose of study drug will be included and all laboratory assessments collected outside of the on-treatment period will be flagged.

A listing of patients with laboratory abnormalities based on normal ranges and notable/extended ranges will also be provided for Safety set 4.

Normal ranges by laboratory parameter will also be provided in a separate listing.

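### For samples taken at age 18 or over, the SAPs recalculate creatinine clearance with Schwartz where the protocol specifies Cockcroft-Gault, and no change table declares it

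*SAP*

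**What the plan says.** Protocol 7.2.4.6.2 (Clinical chemistry) assigns the calculation to the central laboratory (a local one in Egypt), each time serum creatinine is collected, "using the Schwartz formula for patients 17 years and younger and the Cockcroft-Gault formula for patients who turn 18 years old during the study". Section 5.2 expects patients to pass that age on study: "Once in the core phase patients can turn 18 years and still be considered eligible, also for participation in the optional extension phase". Treatment is 48 weeks in the core phase, followed by "an optional extension phase where all patients will receive the granules up to 5 years from entering extension phase".

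Protocol Table 6-2 attaches a dose reduction to "Creatinine clearance between 40 and less 60 mL/min". Below 40 mL/min its instruction is "Deferasirox therapy must be discontinued". Protocol Table 10-1 uses 60 and 40 mL/min as the notable and extended limits, confirmed on two consecutive measurements at least 7 days apart, and calls the variable simply creatinine clearance.

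The SAPs apply the same limits to a recalculated variable. Final SAP Table 2-4 says: "Recalculated creatinine clearance will be calculated using the Schwartz formula (for pediatric population at baseline". Section 5.2.1 repeats it ("The recalculated creatinine clearance will be calculated using the Schwartz formula (pediatric population at baseline") and adds the condition "Schwartz formula (<18 years of age at beginning of the study". The same rule is in section 4.7.2 of SAP Amendment 3 (the primary analysis) and section 4.6.3 of the End of Core SAP. The constant k follows current age, but its top category is 13 years and over, with no upper limit. Each SAP also keeps an MDRD value in the datasets for possible requests. None mentions Cockcroft-Gault.

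The change tables do not cover this. Amendment 3 lists nothing. The End of Core SAP lists average dose, concomitant medication and vital-sign limits. The final SAP lists only exposure-adjusted adverse event incidence.

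**The concern.** The protocol conditions the formula on age at the sample; the SAPs condition it on age at study start. Inclusion criterion 2 requires age under 18, so the SAP condition is true for every patient and stays true however long they remain on study. After the 18th birthday, the clearance that the laboratory reports and the clearance that the tables classify are two different quantities set against the same limits of 60 and 40 mL/min.

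Renal toxicity is actively monitored, and change in creatinine clearance is named in the extension-phase safety endpoint. The final report covers the entire granule period, where samples at 18 or over accumulate. A reader of the final notable/extended table would have no sign that those samples were scored by a formula that the protocol does not use for them.

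**Working it through.** The documents give no count or rate on this point, so there is no stated figure to reproduce. The mismatch follows from the texts alone; its size needs a calculation.

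**Inputs**
- Schwartz, from final SAP 5.2.1: CrCl = k × height / (SCr × 0.01131), with k = 0.55 for girls and 0.70 for boys aged 13 and over, and SCr in µmol/L. Since 1/0.01131 = 88.4, the constant is the µmol/L to mg/dL conversion and the units are consistent.
- Cockcroft-Gault: named in the protocol but not written out. Assumed standard form: (140 − age) × weight / (72 × SCr × 0.01131), times 0.85 for females.
- Heights and weights: illustrative assumptions, shown as a range.

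**Who can be affected**
- Core phase: 18 − 48 × 7/365.25 = 17.1 years or older at enrolment.
- Core plus 5 years: 18 − 48 × 7/365.25 − 5 = 12.1 years or older at enrolment.

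**One patient: woman, 18 years, 150 cm, 45 kg, SCr 97 µmol/L**
- Schwartz: 0.55 × 150 / (97 × 0.01131) = 75.2 mL/min.
- Cockcroft-Gault: 122 × 45 × 0.85 / (72 × 97 × 0.01131) = 59.1 mL/min.
- She falls below 60 at about 96 µmol/L by Cockcroft-Gault and 122 by Schwartz. She falls below 40 at about 143 and 182.

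**Direction**

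Creatinine cancels in the ratio of the two formulas. They agree when weight/height = 72k / (140 − age), with the denominator times 0.85 for females. At age 18:
- Females: 39.6/103.7 = 0.382 kg/cm, so 57 kg at 150 cm and 61 kg at 160 cm.
- Males: 50.4/122 = 0.413 kg/cm, so 66 kg at 160 cm and 70 kg at 170 cm.

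Below these weights Schwartz is the higher value; above them it is the lower.

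| Age 18 | Schwartz when Cockcroft-Gault = 60 | Schwartz when Cockcroft-Gault = 40 |
|---|---|---|
| Male 150 cm, 40 kg | 93 | 62 |
| Male 165 cm, 50 kg | 82 | 54.5 |
| Male 175 cm, 70 kg | 62 | 41 |
| Male 175 cm, 80 kg | 54 | 36 |
| Female 145 cm, 38 kg | 87 | 58 |
| Female 155 cm, 45 kg | 79 | 53 |
| Female 160 cm, 55 kg | 67 | 44 |
| Female 160 cm, 65 kg | 56 | 38 |

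The reverse case is just as concrete. For a male of 175 cm and 80 kg with SCr 185 µmol/L, Schwartz is 0.70 × 175 / (185 × 0.01131) = 58.5, below the notable limit. Cockcroft-Gault is 122 × 80 / (72 × 185 × 0.01131) = 64.8, above it.

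**The case against.** The strongest case for the SAPs is that one formula throughout keeps each patient comparable with their own baseline. Final SAP 2.7.4.2 compares baseline with the worst post-baseline category. If the formula switched inside that comparison, the woman above, with creatinine unchanged at 97 µmol/L, would go from 75 at age 17 to 59 at 18. Two such results at least 7 days apart would make her notable with no renal change. This stands, and it rules out simply substituting Cockcroft-Gault in the shift tables. It does not excuse leaving the departure undeclared, and no SAP gives it as a reason.

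A reader might infer that renal events acted on at sites go uncounted. The documents do not support that. Protocol 8.1.1 and 8.1.2.1 make a laboratory abnormality that requires a change in study drug an adverse event. Final SAP 2.7.1 tabulates adverse events by dose adjustment, interruption and discontinuation, and 2.4.1 summarises dose changes with reasons. The notable serum creatinine category does not depend on either formula. Nor was the notable category ever a mirror of site action: Table 10-1 requires confirmation, and the creatinine clearance rows of Table 6-2 state none.

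A reader might also infer that the laboratory value is thrown away. Protocol Table 7-2 marks creatinine clearance as a database item, the final SAP plans a listing of all laboratory values, and the SAP variable is openly labelled as recalculated.

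**Conclusion.** The conflict between Protocol 7.2.4.6.2 and the three SAPs is explicit and undeclared. For samples at age 18 or over, the creatinine clearance summaries and the notable/extended tables classify a different quantity from the one the protocol defines. The effect can be large for an individual: 75 against 59 mL/min in the example, and at 150 cm and 40 kg a male at 40 mL/min by Cockcroft-Gault would not even reach the <60 category by Schwartz.

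A net claim that the SAP favours the granules by reporting fewer renal events is not supported. The direction reverses at the break-even weight, the documents give no body sizes for patients at 18 or over, and they do not say how many patients reach that age. No rate can be stated.

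The mismatch rests on the texts alone. The magnitudes rest on the assumed standard Cockcroft-Gault form and the illustrative body sizes. The effect is mainly in the extension; in the core phase only patients enrolled from about 17.1 years can contribute. Nothing here says which formula or limit should guide patient management.

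**What to change.** In the final SAP, reconcile section 5.2.1 with Protocol 7.2.4.6.2 in two steps:

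1. Add a row to Table 4-1 stating that clearance is recalculated with Schwartz at all ages, whereas the protocol moves to Cockcroft-Gault at 18, and give the reason.
2. Add a notable/extended table (<60 and <40 mL/min, with the existing confirmation rule) for samples at age 18 or over, using the protocol's formula. It can use either the laboratory-reported value or Cockcroft-Gault derived from age, sex, weight and creatinine. State how many patients and samples contribute.

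Keep this table apart from the Schwartz-based shift and change-from-baseline tables, so that the change of formula at 18 is not read as a change from baseline.

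The cost is one extra table, one age-conditional derivation if the laboratory value is not used, and a presentation split at age 18. No new data collection is needed.

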### 5.2.2 Handling of Special character in Laboratory data

If the values (results and ranges) of the laboratory parameters like Hematology, Biochemistry and urinalysis are provided as '<X' or '>X' (i.e. below limit of detection either lower or upper side), prior to conversion of laboratory values to SI unit, these numeric values are set to X for the analysis purposes, after removing the '</'>' symbol, when generating the tables and figures which are related to above mentioned laboratory parameters e.g., descriptive and shift tables of laboratory parameter. However, in case of listing actual values with '</'>' symbol will be reported.

## 5.3 Time windows

### 5.3.1 Study drug exposure

Study drug will be dispensed at randomization (week 1), then every four weeks. Dose adjustments based on safety are allowed at any time point during the study.

Information on study drug strength will be collected on the Dose Administration Record (DAR) eCRF and includes the planned dose (mg/kg/day), actual total daily dose (mg) taken, reason for the dose change, start date and end date.

[Table 4-3](#) shows the defined study periods for drug exposure.

All assessments within a time period will be used to calculate the drug exposure for the corresponding period.

**Table 4-3 Study periods for drug exposure**

Period	Visit Period Definition
Month 1	Study Day 1 – 28
Month 2	Study Days 29 – 56
Month y (with y=3, 4, 5,...)	Study Days (y-1)*28+1 to (y)*28
Etc.	

\*Study Day 1 = first day of study treatment

### 5.3.2 Laboratory data and vital signs

If two or more assessments are performed within a time window then the assessment closest to the planned visit is used in analyses by time window. When two values are equidistant from the planned assessment, the later one is used in analyses. When multiple values are reported on the same day then the average value is used in analyses. For parameters with categorical results, the one from central laboratory is used in analyses. If multiple values are reported on the same day from local and central laboratory, the central laboratory value is used in analyses. If only local lab assessments are collected, then local lab values are considered for analyses.

For worst post-baseline assessment, all on-treatment values are considered regardless of time windows.

[Table 5-4](#) shows the defined time windows.

**Table 5-4 Time windows for laboratory data, vital signs, weight and BMI**

Time Window	Planned Visit Timing	Time Window Definition
On treatment		
Baseline	On or before Study Day 1*	$\leq$ Study Day 1

Time Window	Planned Visit Timing	Time Window Definition
On treatment		
Week 2**	Study Day* 8	Study Days 2 – 11 (excluded baseline assessment)
Week 3**	Study Day* 15	Study Days 12 – 18
Week 4**	Study Day* 22	Study Days 19 – 25
Week 5	Study Day* 29	Study Days 26 – 42
Every 4 weeks thereafter		
Week $y=5+4*k$ (with $k = 1, 2, 3, 4, 5, 6, 7, 8, 9, 10, 11, 12\dots$ )	Study Day $(5+4*k-1)*7+1$	Study Days $(5+4*k-1)*7+1-14$ to $(5+4*k-1)*7+1+13$ Notes: - EOT data visit are included if obtained within the next 7* days of last non-0 dose intake (*NA for patients continuing in extension phase).

\* Study Day 1 = first day of study treatment

\*\* where appropriate (e.g. week 2 time-window NA for serum ferritin)

